10.3 Clinical Laboratory Evaluation

Laboratory parameters for serum chemistry, hematology, complement, and coagulation will be summarized by dose group in phase 1 and treatment arm in phase 2 using descriptive statistics at baseline and at worst-case post-baseline.

Select laboratory parameters for serum chemistry, hematology, and coagulation will be assigned grades according to NCI Common Terminology Criteria for Adverse Events (CTCAE) v4.03. The complement parameters will be considered being worse if the post-baseline value is lower than baseline value. The worse case post-baseline value will be the lowest value after baseline. Complement parameter results with 50% decrease from baseline may be summarized separately. Shift tables assessing changes from baseline to assigned worst-case post-baseline in assigned CTCAE grade will be summarized. Shift tables will use results from all visits (scheduled and

unscheduled). For laboratory parameters that are not graded by the CTCAE v4.03, shift tables relative to the normal range will be produced and will also use results from all visits (scheduled and unscheduled). The laboratory parameter will be summarized in applicable shift tables (by CTCAE v4.03 grade and/or relative to the normal range). Laboratory parameters that have bidirectional Worst-cases (that is, laboratory parameters which have both CTCAE or normal range shift for low values and for high values) will have the results for both directions reported.

Shift tables will report the counts and percentages of subjects shifting for each dose group for phase 1 and by treatment arm for phase 2.

Plots for each dose level showing the mean complement with standard error bars by visit will be produced for the phase 1 results. For the phase 1 and 2 results combined, these plots will be by treatment arm.

Table 11: CTCAE Toxicity Grades: Hematology

Analyte	Standard Unit	Directional Change	Toxicity Grades (CTCAE v4.03)
Hemoglobin ^[1]	g/dL	Decrease	Grade 1: < LLN – 10 g/dL Grade 2: < 10 – 8 g/dL Grade 3: < 8 g/dL Grade 4: Not defined
		Increase	Grade 1: > ULN – (2+ULN) g/dL Grade 2: > (2+ULN) – (4+ULN) g/dL Grade 3: > 4+ULN g/dL Grade 4: Not defined
Lymphocytes	$\times 10^3/\mu\text{L}$	Decrease	Grade 1: < LLN – $0.8 \times 10^3/\mu\text{L}$ Grade 2: < 0.8 – $0.5 \times 10^3/\mu\text{L}$ Grade 3: < 0.5 – $0.2 \times 10^3/\mu\text{L}$ Grade 4: < $0.2 \times 10^3/\mu\text{L}$
Lymphocytes	$\times 10^9/\text{L}$	Increase	Grade 1: Not defined Grade 2: > 4.0 – $20.0 \times 10^3/\mu\text{L}$ Grade 3: $> 20.0 \times 10^3/\mu\text{L}$ Grade 4: Not defined
Neutrophils	$\times 10^9/\text{L}$	Decrease	Grade 1: < LLN – $1.5 \times 10^3/\mu\text{L}$ Grade 2: < 1.5 – $1.0 \times 10^3/\mu\text{L}$ Grade 3: < 1.0 – $0.5 \times 10^3/\mu\text{L}$ Grade 4: < $0.5 \times 10^3/\mu\text{L}$
Platelets	$\times 10^3/\mu\text{L}$	Decrease	Grade 1: < LLN – $75.0 \times 10^3/\mu\text{L}$ Grade 2: < 75.0 – $50.0 \times 10^3/\mu\text{L}$

WBC	$\times 10^6/\mu\text{L}$	Decrease	Grade 1: $< \text{LLN} - 3.0 \times 10^3/\mu\text{L}$
			Grade 2: $< 3.0 - 2.0 \times 10^3/\mu\text{L}$
		Increase	Grade 3: $< 2.0 - 1.0 \times 10^3/\mu\text{L}$
			Grade 4: $< 1.0 \times 10^3/\mu\text{L}$
			Grade 1: Not defined
			Grade 2: Not defined
			Grade 3: $> 100 \times 10^3/\mu\text{L}$
			Grade 4: Not defined

LLN=lower limit of normal. ULN=upper limit of normal. The LLN and ULN for each analyte will be determined from the normal range of each local laboratory.

[1] For increased hemoglobin results, if the baseline value is above the ULN, the baseline value will be used instead of the ULN to assess grades 1, 2, and 3.

Table 12: CTCAE Toxicity Grades: Coagulation

Analyte	Standard Unit	Directional Change	Toxicity Grades (CTCAE v4.03)
aPTT	sec	Increase	Grade 1: >ULN – 1.5 x ULN Grade 2: >1.5 – 2.5 x ULN Grade 3: >2.5 x ULN Grade 4: Not defined
INR	No units	Increase	Grade 1: >ULN – 1.5 x ULN Grade 2: >1.5 – 2.5 x ULN Grade 3: >2.5 x ULN Grade 4: Not defined

LLN=lower limit of normal. ULN=upper limit of normal. The LLN and ULN for each analyte will be determined from the normal range of each local laboratory.

Table 13: CTCAE Toxicity Grades: Chemistry

Analyte	Standard Unit	Directional Change	Toxicity Grades (CTCAE v4.03)
ALT (SGPT)	U/L	Increase	Grade 1: > ULN – 3.0 x ULN Grade 2: > 3.0 – 5.0 x ULN Grade 3: > 5.0 – 20.0 x ULN Grade 4: > 20.0 x ULN
AST (SGOT)	U/L	Increase	Grade 1: > ULN – 3.0 x ULN Grade 2: > 3.0 – 5.0 x ULN Grade 3: > 5.0 – 20.0 x ULN Grade 4: > 20.0 x ULN
Alkaline Phosphatase	U/L	Increase	Grade 1: > ULN – 2.5 x ULN Grade 2: > 2.5 – 5.0 x ULN Grade 3: > 5.0 – 20.0 x ULN Grade 4: > 20.0 x ULN
Albumin	g/dL	Decrease	Grade 1: < LLN – 3 g/dL Grade 2: < 3 – 2 g/dL Grade 3: < 2 g/dL Grade 4: Not defined
Calcium	mg/dL	Decrease	Grade 1: < LLN – 8.0 mg/dL Grade 2: < 8 – 7.0 mg/dL Grade 3: < 7 – 6 mg/dL Grade 4: < 6 mg/dL
Calcium	mg/dL	Increase	Grade 1: ULN - 11.5 mg/dL Grade 2: > - 11.5 – 12.5 mg/dL

			Grade 3: > 12.5 - 13.5 mg/dL Grade 4: > 13.5 mg/dL
Cholesterol	mg/dL	Increase	Grade 1: >ULN - 300 mg/dL Grade 2: >300 – 400 mg/dL Grade 3: >400 - 500 mg/dL Grade 4: >500 mg/dL
Creatinine	mg/dL	Increase	Grade 1: > ULN – 1.5 x ULN Grade 2: > 1.5 – 3.0 x ULN Grade 3: > 3.0 – 6.0 x ULN Grade 4: > 6.0 x ULN
GGT		Increase	Grade 1 >ULN - 2.5 x ULN Grade 2: >2.5 - 5.0 x ULN Grade 3: >5.0 - 20.0 x ULN Grade 4: >20.0 x ULN
Glucose	mg/dL	Decrease	Grade 1 <LLN - 55 mg/dL Grade 2: <55 – 40 mg/dL Grade 3: <40 - 30 mg/dL Grade 4: <30 mg/dL
Glucose	mg/dL	Increase	Grade 1: <ULN – 160 mg/dL Grade 2: 160- 250 mg/dL Grade 3: <250 - 500 mg/dL Grade 4: <500 mg/dL
Phosphate	mg/dL	Decrease	Grade 1: <LLN – 2.5 mg/dL Grade 2: <2.5 - 2 mg/dL Grade 3: <2 - 1 mg/dL

Grade 4: <1 mg/dL

Potassium*	mEq/L	Decrease	Grade 1: <LLN - 3.0 mEq/L Grade 2: <LLN - 3.0 mEq/L Grade 3: <3 – 2.5. mEq/L Grade 4: <2.5 mEq/L
		Increase	Grade 1 >ULN – 5.5 mEq/L Grade 2: 5.5>- 6 mEq/L Grade 3: >6 - 7 mEq/L Grade 4: >7 mEq/L
Sodium	mEq/L	Decrease	Grade 1: < LLN – 130 mEq/L Grade 2: Not defined Grade 3: < 130 – 120 mEq/L Grade 4: < 120 mEq/L
		Increase	Grade 1: > ULN – 150 mEq/L Grade 2: > 150 – 155 mEq/L Grade 3: > 155 – 160 mEq/L Grade 4: > 160 mEq/L
Total Bilirubin	mg/dL	Increase	Grade 1: > ULN – 1.5 x ULN Grade 2: >1.5 – 3.0 x ULN Grade 3: >3.0 – 10.0 x ULN Grade 4: >10.0 x ULN
			Grade 1 < ULN - 10 mg/dL Not Defined Grade 3 < ULN - 10 mg/dL Grade 4: <10 mg/dL
<hr/>			

LLN=lower limit of normal. ULN=upper limit of normal. The LLN and ULN for each analyte will be determined from the normal range of each local laboratory.

* Indicates laboratory values for which CTCAE grade is not based on the laboratory value; clinical symptoms are also involved.

Urinalysis results will not be summarized but will be listed.

Data listings of laboratory results will be provided for each subject. Laboratory values that are out of the normal range will be flagged in listings, and those that are graded by the CTCAE v4.03 will have the assigned grade included in the listing.

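### The Glucose Increase row of SAP Table 13 has its inequality signs reversed: as printed, every value below 500 mg/dL meets Grade 4 and values above 500 mg/dL meet no grade

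*SAP*

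**What the plan says.** SAP Section 10.3 states that selected laboratory parameters "will be assigned grades according to NCI Common Terminology Criteria for Adverse Events (CTCAE) v4.03", and Table 13 sets out the chemistry limits. Glucose has two rows. The Increase row reads in full: "Grade 1: <ULN – 160 mg/dL Grade 2: 160- 250 mg/dL Grade 3: <250 - 500 mg/dL Grade 4: <500 mg/dL". Its two highest grades, which matter most here, are therefore "Grade 3: <250 - 500 mg/dL Grade 4: <500 mg/dL".

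The use of the grades is also stated in Section 10.3: "Shift tables assessing changes from baseline to assigned worst-case post-baseline in assigned CTCAE grade will be summarized". Parameters with a worst case in both directions, as glucose has, are reported in both. The subject listings carry the assigned grade as well. Appendix E lists the resulting output as Table 14.3.4.3.2.2, the serum chemistry CTCAE shift table.

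**The concern.** The row contradicts itself. Its direction column says Increase and its cut-points climb with grade, but the printed signs select values below the cut-points. A less-than sign belongs in a Decrease row, where the cut-points fall as the grade rises.

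This is the rule from which a programmer would code the grade. If it is followed as printed, the shift table cannot show hyperglycaemia. A subject with 90 mg/dL at baseline and 600 mg/dL at worst would go from Grade 4 to ungraded, so a marked rise would look like an improvement.

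**Working it through.** **Inputs.** The Increase row is taken as quoted above. The SAP takes ULN from each local laboratory and gives no figure, so a glucose ULN of 100 to 125 mg/dL is assumed here. The Grade 4 result does not depend on that assumption.

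**Comparison within Table 13.** The Glucose Decrease row ends "Grade 3: <40 - 30 mg/dL Grade 4: <30 mg/dL". Its cut-points fall and its sign is less-than, which is coherent. The Cholesterol Increase row ends "Grade 3: >400 - 500 mg/dL Grade 4: >500 mg/dL". It has the same top cut-point as the Glucose Increase row, 500 mg/dL, with the opposite sign. Among the labelled Increase rows, only glucose uses a less-than sign.

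**Two ways of coding the row as printed.**

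- Strict: the sign applies to the first number and the second number is the other bound, as in the Decrease rows. Grade 1 is below ULN and at least 160. Grade 2 is 160 to 250. Grade 3 is below 250 and at least 500. Grade 4 is below 500. No value can satisfy Grade 3, and none can satisfy Grade 1 when ULN is 160 or less.
- Lenient: the dash is a span and the sign is ignored in Grades 1 and 3. Grade 1 is above ULN and below 160. Grade 2 is 160 to 250. Grade 3 is above 250 to 500. Grade 4 is still below 500.

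**Repaired.** The cut-points are unchanged and a greater-than sign is used throughout.

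| Glucose, mg/dL | Printed, strict | Printed, lenient | Repaired |
|---|---|---|---|
| 60 | 4 | 4 | none |
| 90 | 4 | 4 | none |
| 100 | 4 | 4 | none |
| 130 | 4 | 1 and 4 | 1 |
| 200 | 2 and 4 | 2 and 4 | 2 |
| 300 | 4 | 3 and 4 | 3 |
| 499 | 4 | 3 and 4 | 3 |
| 500 | none | 3 | 3 |
| 501 | none | none | 4 |
| 600 | none | none | 4 |

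The results are the same for ULN 100 and ULN 125. Under both readings every value below 500 meets Grade 4 and every value above 500 meets nothing. The readings differ at exactly 500, and in whether 130, 300 and 499 also meet a lower grade. Neither gives one grade per value.

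**The case against.** **It would be caught.** The text and the table's column header both name CTCAE v4.03, and Section 5 requires independent validation of the programs and senior review of the output. A row that puts normal glucose in Grade 4 is conspicuous. This stands in part: the harm arises only if the row is coded as printed, and a careful programmer may not do so. But Section 5 also requires output to be checked for consistency with the plan, and here the plan is what is wrong. A programmer who silently corrects the row departs from the SAP, and Section 1 asks for deviations to be documented in the study report.

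**It is a conversion error in the text.** This cannot be wholly excluded, but it is unlikely. Greater-than signs survive in nearby rows, and the less-than sign appears three times in this one.

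**Stronger readings that a reader might infer.**

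- *The last row has the same error and lacks a name.* That row reads "Grade 1 < ULN - 10 mg/dL Not Defined Grade 3 < ULN - 10 mg/dL Grade 4: <10 mg/dL". Its limits run up from ULN to 10 mg/dL, so the signs look reversed. With no analyte or direction shown, that is only an inference, and the blank label may come from PDF conversion. That normal values would be Grade 4 there also needs a ULN of at most 10 mg/dL, which the SAP does not state.
- *All other Increase rows are clean.* They are not. Calcium Grade 1 has no sign, calcium Grade 2 has a stray dash after its sign, and potassium Grade 2 has its sign misplaced. The claim that holds is narrower: none of them uses a less-than sign.
- *Toxicity decisions or immune-related events would be misjudged.* The SAP does not support this. Section 3.1.5 grades toxicity by CTCAE v4.03 directly, the Cohort Review Committee adjudicates DLTs (Section 3.1.4), and immune-related events come from a list of MedDRA codes (Section 10.2). Nothing in the SAP ties glucose grades to endocrinopathy.

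**Conclusion.** The Glucose Increase row is wrong as written, and this can be shown from Table 13 alone. If it is coded as printed, all values below 500 mg/dL meet Grade 4 and all values above 500 mg/dL are ungraded. The effect is confined to one analyte in one direction, in the CTCAE shift table and the listing grades. No DLT rule, stopping boundary or efficacy endpoint uses Table 13. The conclusion assumes that the printed signs are those of the SAP itself. The practical risk depends on whether the programming follows the row literally. The last row and the irregular calcium and potassium signs are matters to check, not established errors of the same kind.

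**What to change.** Keep the printed cut-points and rewrite the Glucose Increase row as: Grade 1 `>ULN – 160`, Grade 2 `>160 – 250`, Grade 3 `>250 – 500`, Grade 4 `>500` mg/dL.

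In the same pass, check three other places against the CTCAE version that the SAP names: the signs in the last row of Table 13, calcium-increase Grades 1 and 2, and potassium-increase Grade 2. Confirm that the last row carries an analyte and a direction in the source file.

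The cost is four grade entries for glucose and a short check of the others. No analysis, population or sample size changes. If grading programs already exist, confirm how this row was coded.

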10.4 Vital Signs

Vital signs (weight, blood pressure, heart rate, respiratory rate, and body temperature) will be summarized by dose group and treatment arm using descriptive statistics at baseline and at worst-case post-baseline. Changes from baseline at worst-case post-baseline relative to the normal range will also be summarized. The worst case post-baseline for weight, blood pressure, heart rate, and respiratory rate will be derived in two directions by their highest increase and decrease respectively.

Diastolic BP and Systolic BP will be assigned grades according to NCI Common Terminology Criteria for Adverse Events (CTCAE) v4.03. Shift tables assessing changes from baseline to Worst-case assigned post-baseline in CTCAE grade will be presented.

Table 14: CTCAE Toxicity Grades: Vital Signs

Vital	Standard Unit	Directional Change	Toxicity Grades (CTCAE v4.03)
Diastolic BP	mm Hg	Increase	Grade 1: 80 - 89
			Grade 2: 90 - 99
			Grade 3: >=100
Systolic BP	mm Hg	Increase	Grade 1: 120 - 139
			Grade 2: 140 - 159
			Grade 3: >=160

--	--	--	--

In addition, shift table assessing changes from baseline to worst decrease post-baseline, in normal range will be summarized for temperature.

Table 15: Normal Range Vital Signs

Vital	Standard Unit	Range
Temperature	F	Low : < 60
		Normal: 60 -100
		High: > 100

Data listings of vital signs will be provided for each subject.

10.5 Physical Examination

Physical examination results will be included in data listings only.

10.6 Electrocardiogram

QTcF in msec will be calculated using the following formula for all subjects:

$$\text{QTcF} = \text{QT}/(\text{RR})^{0.33}.$$

Overall interpretation results for ECG will be summarized using shift tables (Normal, Abnormal NCS, Abnormal CS) comparing baseline to follow-up. Descriptive statistics at baseline and at Worst-case post-baseline as well as changes from baseline will be summarized QTcF.

In addition, a categorical summary of abnormal QTcF values will be presented.

- At each visit, the number of subjects with QTcF values of > 450 ms, > 480 ms, and > 500 ms will be presented.
- At each post-baseline visit, the number of subjects with change from baseline values in QTcF of > 30 ms and > 60 ms will be presented.

Frequency counts and percentages of subjects shifting from baseline status at worst decrease post-baseline subjects will be summarized; subjects with missing baseline or missing post-baseline result will also be summarized. The shift will be based on QTcF range (≤ 450 , > 450 to ≤ 480 , > 480 to ≤ 500 , > 500 msec).

A scatterplot of the baseline and worst-case on-treatment QTcF measures will be produced. Reference lines at equivalence (i.e., 45°), an increase of 30 ms, and an increase of 60 ms, as well as absolute references lines at 450 and 500 ms for both axes, will be included.

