⁹ CBC with differential should be done 24 to 48 hours after the IMO-2125 injection, to coincide with the post-injection biopsy (if the biopsy is conducted). Chemistry profile and coagulation tests do not have to be conducted if Screening tests were conducted within 7 days of the Cycle 1 Week 1 Visit.

¹⁰PT, aPTT, INR.

¹¹ Blood pressure, heart rate, respiratory rate, and temperature.

¹² Week 2 ECG pre-dose and at 2 hours post-IMO-2125 administration. Week 11 ECG at 2 hours post-IMO-2125 administration.

¹³ Including assessment of melanoma lesions.

¹⁴ In Phase 2, all tumor biopsies are optional. See Section 13.2 of the protocol and the Laboratory Manual for details on the collection of biopsies and analyses of biomarkers.

¹⁵ Biopsy of the injected tumor should occur within 24 to 48 hours after injection (no more than 48 hours).

¹⁶ In Phase 2, blood biomarker samples will be collected from at least 20 patients treated at the IMO-2125 RP2D after which the Sponsor will determine if additional samples are needed. The blood biomarker samples will be collected on Day 1 before IMO-2125 administration, 4 hours after IMO-2125 administration, and 24 to 48 hours (coinciding with the 24-hour PK sample) after the injection. At Week 2 and Cycle 3 Week 8, collect before ipilimumab or pembrolizumab dosing.

¹⁷ Radiologic assessment and Investigator assessment of response at Week 8, Week 17, and Week 29 may be conducted within a \pm 7-day window.

¹⁸ At least every 3 months until progression, start of next melanoma treatment, withdrawal of consent, death, or Sponsor notification that follow up is no longer required.

¹⁹ In Phase 2, response assessed using irRECIST and RECIST v 1.1. Best response to first subsequent treatment should also be captured. Confirmatory scans for CR, PR, and progressive disease should be performed \geq 4 weeks after the date the response was first documented.

²⁰ To minimize bias in the PRO data, the PRO assessments should be completed before study drug administration and AE assessments.

²¹ For patients assigned to the IMO-2125 + pembrolizumab treatment arm, continued pembrolizumab dosing per the approved product label is permitted at the discretion of the Investigator.

²² PK: blood sampling for analysis of plasma concentrations of IMO-2125 and serum concentrations of ipilimumab, and pembrolizumab (See **Error! Reference source not found.**Table 3 of the protocol for specific collection

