8.3 Baseline, Worst, and Best-case Post-Baseline Values

Unless otherwise noted, baseline is defined as the last non-missing value recorded before the first dose of study drug. Unscheduled visits will be used in the determination of baseline values, when applicable.

Worst-case post-baseline values will be identified from all scheduled and unscheduled visits. For measures with degradation from both increases and decreases, Worst-cases will be identified and summarized for both.

Best-case post-baseline values will be identified from all scheduled and unscheduled visits. For measurable tumor assessment Best-case will be identified as the largest decrease, or, for subjects who have no decrease, the smallest increase in post-baseline assessment.

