	14.3.2.2.3	Pembrolizumab-Related Serious Treatment-Emergent Adverse Events by Preferred Term (Safety Population)
	14.3.2.4	Treatment-Emergent Adverse Events with CTCAE Grade 3 or Higher by Preferred Term (Safety Population)
	14.3.3.5	Treatment-Emergent Adverse Events Leading To Discontinuation by Preferred Term (Safety Population)
	14.3.2.6.1	Treatment-Emergent Adverse Events of Action Taken with IMO-2125 as Drug Withdrawn by Preferred Term (Safety Population)
	14.3.2.6.2	Treatment-Emergent Adverse Events of Action Taken with Ipilimumab as Drug Withdrawn by Preferred Term (Safety Population)
	14.3.2.6.3	Treatment-Emergent Adverse Events of Action Taken with Pembrolizumab as Drug Withdrawn by Preferred Term (Safety Population)
	14.3.3.7	Immune-Related Treatment-Emergent Adverse Events by Preferred Term (Safety Population)
	14.3.3.8	Treatment-Emergent Adverse Events with Fatal Outcome by Preferred Term (Safety Population)
14.3.4		Laboratory
	14.3.4.1.1	Hematology (Safety Population)
	14.3.4.1.2.1	Hematology – Shift from Baseline Relative to the Normal Range (Safety Population)
	14.3.4.1.2.2	Hematology – CTCAE Shift from Baseline (Safety Population)
	14.3.4.2.1	Coagulation (Safety Population)
	14.3.4.2.2.1	Coagulation – Shift from Baseline Relative to the Normal Range (Safety Population)
	14.3.4.2.2.2	Coagulation – CTCAE Shift from Baseline (Safety Population)
	14.3.4.3.1	Serum Chemistry (Safety Population)
	14.3.4.3.2.1	Serum Chemistry – Shift from Baseline Relative to the Normal Range (Safety Population)
	14.3.4.3.2.2	Serum Chemistry – CTCAE Shift from Baseline (Safety Population)
	14.3.4.4.1	Complement Testing (Safety Population)

ICH Heading	Table Number	Table Description
	14.3.4.4.2	Complement Testing – Shift from Baseline Relative to the Normal Range (Safety Population)
	14.3.4.4.3	Complement Testing – $\geq 50\%$ Decrease from Baseline (Safety Population)
14.3.5		Extent of Exposure
	14.3.5.1.1	Study Drug (IMO-2125) Exposure (Safety Population)
	14.3.5.1.2	Ipilimumab Exposure (Safety Population)
	14.3.5.1.3	Pembrolizumab Exposure (Safety Population)
	14.3.5.2.1	Dose Modifications for Study Drug (IMO-2125) (Safety Population)
	14.3.5.2.2	Dose Modifications for Ipilimumab (Safety Population)
	14.3.5.2.3	Dose Modifications for Pembrolizumab (Safety Population)
14.3.6		Vital Signs
	14.3.6.1	Vital Signs (Safety Population)
	14.3.6.2	Vital Signs – Shift from Baseline Relative to the Normal Range (Safety Population)

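### The QTcF and temperature shift tables use each subject's lowest post-baseline reading, so a rise appears only if every reading is raised

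*SAP*

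**What the plan says.** Section 10.6 of the SAP defines the QTcF shift table by this sentence: "Frequency counts and percentages of subjects shifting from baseline status at worst decrease post-baseline subjects will be summarized". It continues, "The shift will be based on QTcF range", and gives four categories: up to 450, above 450 to 480, above 480 to 500, and above 500 ms.

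Section 10.4 takes the worst case in both directions for weight, blood pressure, heart rate and respiratory rate. Body temperature is not in that list. The section then adds a "shift table assessing changes from baseline to worst decrease post-baseline, in normal range will be summarized for temperature". Table 15 supplies the categories: Low below 60 F, Normal 60 to 100 F, High above 100 F. A sentence covering all vital signs states no direction for temperature: "Changes from baseline at worst-case post-baseline relative to the normal range will also be summarized".

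The general rule in Section 8.3 is: "For measures with degradation from both increases and decreases, Worst-cases will be identified and summarized for both".

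In Table 13 (Section 10.3), the glucose row with direction Increase contains "Grade 3: <250 - 500 mg/dL Grade 4: <500 mg/dL".

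**The concern.** For QTcF the selected value and the categories point in opposite directions. Every cut-point is an upper limit, and the other directional QTcF outputs in Section 10.6 look for increases: by-visit counts above 450, 480 and 500 ms, changes above 30 and 60 ms, and scatterplot lines at +30 and +60 ms. The shift table alone takes the reading least likely to show prolongation.

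For temperature, Table 15 has both a Low and a High category, so the SAP itself treats the measure as able to worsen either way. Section 8.3 would then require both directions, yet the specific sentence names only the decrease. Fever matters to this trial's safety review: Section 3.1.5 uses it in a hematologic DLT criterion.

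Two table entries nearby are also wrong. The lower normal limit for temperature is not a plausible body temperature, and the glucose-increase signs contradict their own direction column.

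**Working it through.** The SAP gives no figure on this point, so there is none to reproduce.

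**1. What the rule selects.** Let b be the baseline and x1 to xk the post-baseline readings. The largest decrease is min(xi − b) = min(xi) − b, because b is fixed. The tabulated value is therefore min(xi), and min(xi) > c only if every xi > c. This is logic and needs no model.

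**2. QTcF readings.** The Phase 2 schedule (Table 5, footnote 12) reads "Week 2 ECG pre-dose and at 2 hours post-IMO-2125 administration. Week 11 ECG at 2 hours post-IMO-2125 administration", and the table adds one ECG at the Week 32 safety follow-up, 21 days after the last IMO-2125 dose. Baseline is the last value before the first dose (Section 8.3), so all four readings are post-baseline. Two of them, Week 2 pre-dose and safety follow-up, are not taken shortly after a dose. A rise above 450 ms at both 2-hour readings that is absent at either of the other two is classed as ≤450.

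Two assumed subjects, each with baseline 430 ms:

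| Post-baseline QTcF (ms) | At the lowest value | At the highest value |
|---|---|---|
| 428, 505, 440, 432 | 428: ≤450, no shift | 505: >500, change +75 |
| 455, 505, 470, 460 | 455: >450 to ≤480 | 505: >500, change +75 |

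The second row shows that even when all readings are raised, the table understates how far.

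**3. Temperature readings.** Table 5 schedules vital signs at Weeks 2, 3, 5, 8, 11, 17, 23, 29 and 32, which is nine visits after Week 1. High requires all available readings to exceed 100 F. An assumed subject with baseline 98.2 F and readings 97.6, 102.4 and 98.0 F is Normal to Normal at the lowest value and Normal to High at the highest. Section 8.3 also counts unscheduled visits, and each extra reading makes an upward shift harder to reach.

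**4. Illustration of the gap.** Assume each reading is raised independently with probability p (not an SAP figure). The chance of being shown as shifted upward is p^k at the lowest value and 1 − (1 − p)^k at the highest.

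| p | QTcF, k = 4: lowest / highest | Temperature, k = 9: lowest / highest |
|---|---|---|
| 0.1 | 0.01% / 34.4% | <0.001% / 61.3% |
| 0.3 | 0.8% / 76.0% | 0.002% / 96.0% |
| 0.5 | 6.3% / 93.8% | 0.2% / 99.8% |
| 0.9 | 65.6% / 99.99% | 38.7% / >99.99% |

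A rise present at nearly every reading can still appear; an intermittent one almost never does.

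**5. Table 15.** (60 − 32) × 5/9 = 15.6 C and (100 − 32) × 5/9 = 37.8 C. The Low cell will be empty in practice, so a table built on the lowest temperature cannot show a low temperature either.

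**6. Table 13, glucose increase.** Read literally, any glucose below 500 mg/dL meets Grade 4, including normal values. Other increase rows, such as ALT, creatinine and sodium, use the greater-than sign.

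**The case against.** QTcF prolongation is not lost from the report. The by-visit counts, the change counts and the scatterplot all show it, and the phrase looks like carried-over wording. That stands and limits the consequence. It does not make the table right: Section 5 requires programs to be checked for consistency with the plan, so a faithful program would pass validation and yield a shift table that disagrees with the by-visit counts.

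For temperature, the decrease-only sentence is introduced as an additional output, and the general sentence on the normal range could be read with Section 8.3 to cover increases. Appendix E allows tables to be split or combined, and the shells are in a separate document. This partly stands: the loss of fever information is possible, not proven. However, Appendix E lists a single vital-sign normal-range shift table (14.3.6.2), and Table 15 defines a range for temperature alone, so the two sentences probably describe one output. If Section 8.3 does govern, the specific sentence contradicts it.

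The probabilities assume independence and complete attendance. Correlated readings and early discontinuation would narrow the gap. That is accepted; they illustrate the logic and do not predict the trial's results.

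The glucose signs and the 60 F limit are separate table-entry errors and do not bear on the direction of the shift tables. They are included because they sit in the same safety sections and can be corrected in the same edit.

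**Conclusion.** The point holds. As written, both shift tables record an upward move only when every post-baseline reading is raised. For QTcF this gives an uninformative table that can conflict with other outputs in the same section. For temperature, intermittent fever may be visible only in adverse event tables and listings; that consequence depends on the probable, but not certain, reading that Table 14.3.6.2 is the only normal-range output. The core conclusion needs no assumption beyond taking the largest decrease to mean the lowest reading. The 60 F limit and the glucose signs are wrong on the face of the document. No efficacy test, DLT rule or stopping boundary is affected. The SAP should be corrected before the tables are programmed.

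**What to change.** - **Section 10.6:** define the QTcF shift table at the highest post-baseline QTcF.
- **Section 10.4:** add body temperature to the two-direction sentence, run its shift table for both the worst increase and the worst decrease, and state whether this is the same output as the normal-range summary (Table 14.3.6.2).
- **Table 15:** replace the 60 F limit with a physiologically plausible lower limit of normal and state its source.
- **Table 13:** in the glucose-increase row, correct the reversed signs to greater-than so that they match the direction column.

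The cost is SAP wording and, where the shells follow it, edits to the table shells. No new data are needed.
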